8.4.2 Capecitabine: Dose modification and treatment for skin toxicity

Emollients such as Diprobase are helpful for hand-foot syndrome (HFS) (also known as hand-foot skin reaction or palmar-plantar erythrodysaesthesia).

HFS dose modifications:	Appearance of toxicity										
Toxicity (CTCAE v3) Grade	1st	2nd	3rd	4th							
	Interrupt until ≤ grade 1 and restart at										
2	100%	75%	50%	Stop							
3	75%	50%	Stop								

Dose modifications should be made as indicated in the chart below.

Figure 4: Capecitabine dose modifications for hand foot syndrome

8.4.3 Cetuximab: General principles of dose modification

Cetuximab dose reductions are permanent. Patients must discontinue cetuximab if more than 2 consecutive infusions are withheld.

8.4.4 Cetuximab: Dose modification for infusion related toxicity

If the patient experiences a mild or moderate infusion-related reaction, the infusion rate may be decreased. It is recommended to maintain this lower infusion rate in all subsequent infusions. Severe infusion-related reactions have been reported in patients treated with cetuximab (see side effects Section 8.2.3). Symptoms usually occur during the first infusion and up to 1 hour after the end of the infusion.

Occurrence of a severe infusion-related reaction requires immediate and permanent discontinuation of cetuximab therapy.

In each case of allergic/hypersensitivity reaction, the investigator should implement treatment measures according to the best available medical practice. Based on previous experience with cetuximab allergic/hypersensitivity reactions, the treatment guidelines as described in Figure 7 may be applicable (below).

CTCAEv3.0 Grade Allergic/ Hypersensitivity Reaction	Treatment
Grade 1	Decrease the cetuximab infusion rate by 50% and monitor closely for any worsening. The total infusion time for cetuximab should not exceed 4 hours.
Grade 2	Stop cetuximab infusion. Administer bronchodilators, oxygen, etc. as medically indicated. Resume infusion at 50% of previous rate once allergic/hypersensitivity reaction has resolved or decreased to Grade 1 in severity, and monitor closely for any worsening
Grade 3 or Grade 4	Stop the cetuximab infusion immediately and disconnect infusion tubing from the subject. Administer epinephrine, bronchodilators, antihistamines, glucocorticoids, intravenous fluids, vasopressor agents, oxygen, etc., as medically indicated. Subjects must be withdrawn immediately from the treatment and must not receive any further cetuximab treatment.

Figure 5: Treatment adjustment in the event of cetuximab caused allergic/hypersensitivity reaction.

Re-treatment following allergic/hypersensitivity reactions:

Once a cetuximab infusion rate has been decreased due to an allergic/hypersensitivity reaction, it will remain decreased for all subsequent infusions. If the subject has a second allergic/hypersensitivity reaction with the slower infusion rate, the infusion should be stopped and cetuximab should be discontinued. If a subject experiences a Grade 3 or 4-allergic/hypersensitivity reactions at any time, cetuximab should be discontinued.

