Mild or moderate reactions (grade 1 or 2) include symptoms such as fever, chills, nausea, rash or dyspnoea. Severe hypersensitivity reactions (grade 3 or 4) usually occur during or within 1 hour of the initial cetuximab infusion, but may occur after several hours or with subsequent infusions, therefore it is recommended to warn patients of the possibility of late onset infusion-related reactions and instruct them to contact their physician. Symptoms include the rapid onset of airway obstruction (bronchospasm, stridor, hoarseness, difficulty in speaking), urticaria, and/or hypotension.

Recently the MABEL study has demonstrated that premedication with corticosteroids can reduce the rate of infusion related reactions for patients receiving cetuximab (see Section 8.2.3 above).

Conjunctivitis may be expected in approximately 5% of patients. Dyspnoea has been reported in 25% of patients with end stage colorectal cancer.

Skin reactions will develop in more than 80% of patients: approximately 15% of these are severe (\geq grade 3). They mainly present as acne-like rash affecting face, upper chest and back. On longer term therapy paronychia can develop in approximately 10% of patients and can be painful. The majority of skin reactions develop within the first 1-3 weeks of therapy. They generally resolve, without sequelae, following the cessation of treatment if the recommended adjustments in dose regimen are followed (see dose modifications Section 8.4.4-8.4.6).

Cetuximab precautions: Cetuximab is contraindicated in patients with known severe (grade 3 or 4) hypersensitivity reactions to cetuximab. There are no specific drug interactions documented with cetuximab. However, any agent that may interfere with the immune system of the patient should preferably be avoided except the indicated study regimen and necessary supportive treatment (including corticosteroids, antiemetics etc).

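### Section 8.4.4 gives two different first actions for a grade 2 cetuximab infusion reaction and two statuses for the reduced rate afterwards, and it points to the wrong figure

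*Protocol*

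**What the plan says.** Section 8.4.4 deals with cetuximab infusion reactions in three places.

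- **Opening text.** "If the patient experiences a mild or moderate infusion-related reaction, the infusion rate may be decreased". The next sentence recommends, without requiring, that the lower rate be kept for later infusions. A severe reaction ends cetuximab permanently.
- **Figure 5**, by CTCAE grade. Grade 1: "Decrease the cetuximab infusion rate by 50% and monitor closely for any worsening". Grade 2: "Stop cetuximab infusion. Administer bronchodilators, oxygen, etc. as medically indicated", and then "Resume infusion at 50% of previous rate once allergic/hypersensitivity reaction has resolved or decreased to Grade 1 in severity". Grade 3 or 4: stop, treat, and give no more cetuximab.
- **Re-treatment paragraph.** Once the rate has been lowered, "it will remain decreased for all subsequent infusions". A second reaction at the reduced rate ends cetuximab.

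Section 8.2.3 links the words to the grades: "Mild or moderate reactions (grade 1 or 2) include symptoms such as fever, chills, nausea, rash or dyspnoea".

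The text introduces the table by saying that "the treatment guidelines as described in Figure 7 may be applicable (below". The table that follows is captioned "Figure 5: Treatment adjustment in the event of cetuximab caused allergic/hypersensitivity reaction". Figure 7, in section 8.4.8, is the acute gastrointestinal toxicity table, graded by diarrhoea.

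**The concern.** A moderate reaction is grade 2 by the protocol's own mapping. Someone following the opening text may slow the infusion, and need not interrupt it. Someone following Figure 5 interrupts it first. Both instructions stand in one short section, and staff would consult it while a reaction is in progress.

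The status of the later rate also matters, because a rule for ending treatment rests on it. Cetuximab ends after a second reaction at the reduced rate. If the reduction is optional and keeping it is only advised, a second reaction could occur at the full rate and fall outside that wording.

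There is a compliance side too. Section 14.2 lists a dose modification that was not observed after an adverse reaction among the matters to be raised urgently with a site, and section 16.1 requires deviations to be notified immediately. Neither can be applied evenly when one section supports both actions.

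**Working it through.** The main check is a comparison of text.

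**Step 1: grade.** Section 8.2.3 puts mild or moderate at grade 1 or 2, so moderate is grade 2.

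**Step 2: the instructions side by side.**

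| | Opening text, 8.4.4 | Figure 5 or re-treatment paragraph |
|---|---|---|
| Grade 1, first action | Rate reduction permitted, amount not stated | Halve the rate |
| Grade 2, first action | Rate reduction permitted, no interruption mentioned | Stop, treat, resume at half rate once resolved or grade 1 |
| Rate at later infusions | Keeping the lower rate is recommended | Lower rate stays |
| Grade 3 or 4 | Permanent discontinuation | Permanent discontinuation |

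The grade 3 or 4 rows agree. The grade 2 row differs in the immediate action and in whether the wording permits or directs. The later-rate row differs in force.

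**Step 3: the rule for a second reaction.** Take a patient with a first grade 2 reaction, then a second non-severe reaction at a later infusion.

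- Under Figure 5 and the re-treatment paragraph, the later infusion runs at the reduced rate. The second reaction therefore meets the condition and cetuximab ends.
- Under the opening text, the rate might not have been lowered, or might have been restored. A second reaction at full rate does not meet the condition as worded.

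The same clinical history can therefore lead to different decisions, depending on which sentence the site followed.

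**Step 4: the figure number.** The text names Figure 7 and places it below. The table directly below is Figure 5. Figure 7 covers another toxicity, four subsections later.

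**Step 5: how many patients.** Section 8.2.3 gives hypersensitivity reactions in about 5% of patients, about half of them severe. The target is 80 patients.

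- Grade 1 or 2: 5% × (1 − 0.5) = 2.5%
- 2.5% × 80 = 2 patients

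The protocol does not split grade 1 from grade 2, so the expected number at grade 2 lies between 0 and about 2.

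**Step 6: dose.** Halving the rate doubles the duration: 2 hours ÷ 0.5 = 4 hours for the loading infusion and 1 hour ÷ 0.5 = 2 hours for the weekly one. Four hours is within the limit in Figure 5's grade 1 row. Slowing the rate does not itself change the dose per square metre.

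**The case against.** The strongest reply is that the opening sentence is a general summary of grades 1 and 2 and the table supplies the detail for each grade. The text never says in so many words that the infusion continues at grade 2. Figure 5's stop is temporary, so a patient can end on a slower infusion by either route. Figure 5 is itself introduced as guidance that might apply, under an instruction to treat according to best medical practice. On the later rate, both sentences point the same way and differ only in strength.

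Much of this stands. It softens the conflict but does not remove it. A site that follows the text need neither interrupt at grade 2 nor keep the slower rate. The table's rows are written as directions, and the re-treatment paragraph carries no such qualification. The change of term between infusion-related and hypersensitivity reaction does not separate the two rules either: section 8.2.3 discusses both as one topic on one grade scale.

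A reader might infer more than the documents support:

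- **That Figure 5 ends cetuximab at grade 2.** It does not; it provides for resumption.
- **That Figure 7 contradicts Figure 5 because it keeps cetuximab at full dose at grade 3.** That row concerns grade 3 diarrhoea, a different toxicity. The pointer also says the table is below, and the next item is plainly the hypersensitivity table. The error is editorial.
- **That reported cetuximab exposure is affected.** Both routes change the rate and not the prescribed dose, and cetuximab exposure is not a listed endpoint.
- **That most of these patients would react at the loading dose.** Section 8.2.3 gives that timing for severe reactions, and in section 8.4.4 the timing sentence follows the one on severe reactions. Neither gives it for mild or moderate ones.

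**Conclusion.** The inconsistency is real and narrow. Section 8.4.4 differs from its own Figure 5 on the immediate action at grade 2, and from its own re-treatment paragraph on whether the lower rate is advised or fixed. The rule for ending cetuximab after a second reaction depends on the latter. The reference to Figure 7 is a numbering mistake.

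About 2 of 80 patients would have a grade 1 or 2 reaction, and no more than that a grade 2 reaction. This rests on the protocol's 5% and one-half applying here, which is uncertain. Section 8.2.3 also reports severe reactions in 1.1% of patients given an antihistamine plus a corticosteroid, against 7.1% with an antihistamine alone, and it recommends the combination for this trial. It gives no corresponding rates for mild or moderate reactions.

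There is no effect on the R0 resection rate, the sample size or the error rates. The point merits correction because it concerns an acute safety instruction for a trial drug.

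**What to change.** The sponsor's clinical team should reconcile the opening text of section 8.4.4, Figure 5 and the re-treatment paragraph so that:

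1. a grade 2 reaction has one instruction for the immediate action;
2. the reduced rate at later infusions has one status, recommended or required, and the second-reaction rule is worded to match;
3. the reference to Figure 7 reads Figure 5.

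Which clinical rule stands is for that team to decide. The cost is a wording amendment, with the usual approval and circulation to sites. No analysis or sample size changes.

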8.4.5 Cetuximab: Dose modification and treatment for skin toxicity

If pruritus occurs an oral antihistamine is advised. Dry skin often occurs (and may contribute to pruritus) general advice on replacing soap with oil for washing, avoidance of hot water for baths or showers and use of emollient creams are beneficial. Fissures may occur in dry skin and topical dressings (e.g. hydrocolloid dressings and as advised by your dermatologist) are helpful.

Discussion with a local dermatologist prior to study initiation would be helpful to agree local plans of management and mechanisms for rapid referral in case of severe skin toxicity.

[figure not shown]
Dose modifications are summarised on the algorithm below. For CTC grade 1 or 2: continue treatment with cetuximab.

It is most important that oral and topical therapy is commenced as soon as the patient experiences signs of cetuximab skin related toxicity. Systemic antibiotics (e.g. a second generation tetracycline such as doxycycline 100mg po daily) should be used and addition of a topical steroid or combination steroid and antibiotic cream should be considered (as duration of therapy is short). Colloidal oatmeal cream or lotion can also be effective.

If grade 3 skin toxicity occurs for a second and third time, cetuximab therapy may again be delayed for up to 14 days with concomitant dose reductions to 200mg/m² and then 150mg/m². Cetuximab dose reductions are permanent. Patients must discontinue cetuximab if more than 2 consecutive infusions are withheld. If the toxicity resolves to grade 2 or less by the following treatment period, treatment may be resumed.

Nail toxicities occur in 8% of patients with cetuximab, characterised by a paronychial inflammation with associated swelling of the lateral skin folds of toes and fingers, especially great toes and thumbs, which may be painful. It may persist for up to three months after cessation of cetuximab therapy. Dermatological advice should be sought. Use of daily salt baths and local antiseptic / astringent ointments have been found to be helpful. Anti-inflammatory drugs may help to ease the pain.

Cetuximab modification flowchart

* These refer to the second and third consecutive week of non-resolving grade 3 skin toxicity Figure 6: Flowchart for cetuximab modification due to skin toxicity

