8.2.3 Cetuximab

Administration: Cetuximab is given intravenously as a 2 hour infusion at 400 mg/m² one week prior to the commencement of radiotherapy. It is then given and as a 1 hour infusion at 250 mg/m² once per week during weeks 1, 2, 3, 4 and 5 of radiotherapy. There is to be equal spacing between infusions.

Cetuximab must be administered under the supervision of a physician experienced in the use of antineoplastic medical products. Close monitoring is required during the infusion and for at least one hour after the end of the infusion. Availability of resuscitation equipment must be ensured.

Prior to cetuximab infusion, patients must receive premedication with an antihistamine (e.g. chlorpheniramine). Recently the MABEL study has demonstrated that the rate of severe (grade 3 and 4) infusion-related reactions in patients receiving cetuximab was 7.1% for 422 patients receiving premedication with an antihistamine alone versus 1.1% for 700 patients receiving any antihistamine plus a corticosteroid (Siena et al,'07). In the light of these data it is recommended that patients within the EXCITE trial should receive premedication using a corticosteroid, for example 8 mg of intravenous dexamethasone, in addition to an antihistamine.

Drug supply: Drug supply of cetuximab will be from special trial stock. The trial centre will inform Merck when all necessary approvals for a centre have been received. Centres should arrange initial supplies once their first patient is screened. Further supplies will be coordinated by hospital pharmacies directly with Merck using a drug request form. The monoclonal antibody is supplied at a concentration of 5mg/ml. The starting dose is 400mg/m² (=80ml/m²). 'Clinical trial' labelling will be provided by Merck in compliance with

regulatory requirements and additional accountability records need to be maintained by the pharmacy.

At the end of the trial the CTC will inform participating sites of the procedure for unused drug return/destruction.

Cetuximab side effects: In approximately 5% of patients hypersensitivity reactions may occur during treatment with cetuximab, approximately half of these reactions being severe.

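### Section 8.4.5 and its Figure 6 footnote appear to set different triggers for the cetuximab reductions to 200 and 150 mg/m²: recurrence of grade 3 skin toxicity in the text, persistence of one episode in the footnote

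*Protocol*

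**What the plan says.** The planned weekly dose of cetuximab after the loading dose is set in section 8.2.3: "It is then given and as a 1 hour infusion at 250 mg/m² once per week", in each of the five weeks of radiotherapy. Section 8.2.1 counts six infusions in all, one loading and five weekly.

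Section 8.4.5 governs skin toxicity. It introduces the flowchart with "Dose modifications are summarised on the algorithm below", so text and figure are meant to state one rule. The text then says "If grade 3 skin toxicity occurs for a second and third time, cetuximab therapy may again be delayed for up to 14 days". The dose falls at the same time, first to 200 and later to 150 mg/m². It adds that "Cetuximab dose reductions are permanent" and gives the condition for restarting: "If the toxicity resolves to grade 2 or less by the following treatment period, treatment may be resumed". Section 8.4.3 sets the limit on missed doses, which 8.4.5 repeats: "Patients must discontinue cetuximab if more than 2 consecutive infusions are withheld".

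The footnote under the flowchart (Figure 6) explains its asterisk: "These refer to the second and third consecutive week of non-resolving grade 3 skin toxicity".

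**The concern.** The text counts episodes. A second or third occurrence, with cetuximab delayed again, presupposes an earlier episode that was managed and ended. The footnote counts weeks within one episode that has not ended. A rash that has cleared and come back is not unresolved over consecutive weeks, and a rash that has never cleared has not occurred a second time. Nothing else in the protocol reconciles the two.

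Cetuximab is the agent added to the irinotecan and capecitabine regimen of the preceding trial (section 2.9), and skin reactions are its most frequent listed side effect in section 8.2.3. Only five weekly doses are planned and reductions are not reversed, so a difference in trigger carries through every infusion that remains. At stake are uniform delivery of the agent under test and uniform safety handling. The R0 endpoint, its denominator, the sample size and the error rates are not affected.

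**Working it through.** The protocol gives no figure to reproduce here. The check applies each trigger to the same patient courses and then bounds the number of patients concerned.

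**Inputs**
- Weekly dose 250 mg/m² (8.2.3); reduced levels 200 and 150 mg/m² (8.4.5).
- Text trigger: second and third occurrence. Footnote trigger: second and third consecutive week without resolution (both 8.4.5).
- Restart at grade 2 or less (8.4.5); discontinuation once more than two consecutive infusions are withheld (8.4.3, 8.4.5).
- Skin reactions in more than 80% of patients, about 15% of these severe, meaning grade 3 or higher (8.2.3).
- Recruitment target 80 (section 13).

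**Assumptions.** (i) The asterisk in Figure 6 marks the 200 and 150 mg/m² steps. (ii) A first episode carries no reduction; the visible text gives none, but the flowchart might.

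**Relative dose at each step:** 200/250 = 80%; 150/250 = 60%.

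**Courses under each trigger**

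| Course | Text (recurrence) | Footnote (persistence) |
|---|---|---|
| Grade 3 resolves, treatment restarts, grade 3 recurs | Second occurrence: 200 mg/m², permanent | First week of a new episode: no reduction |
| A third separate episode, each resolving before its second week | 150 mg/m², permanent | No reduction |
| One episode, unresolved in its second week, then resolves | First occurrence: 200/150 rule not reached | First marked step: 200 mg/m², permanent |
| One episode, unresolved for three weeks, infusion withheld each week | Third consecutive infusion withheld: discontinue | Same limit applies: discontinue |

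The first three rows differ. The fourth does not: infusions are weekly, so three unresolved weeks with every dose withheld is three consecutive infusions, which exceeds two whichever trigger is used.

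**Number of patients.** 0.80 × 0.15 = 0.12, and 0.12 × 80 = 9.6, about 10 patients with a severe skin reaction. The 80% is stated as a lower limit; at its logical maximum of 100%, 1.00 × 0.15 × 80 = 12. The triggers diverge only for those whose grade 3 reaction recurs or lasts into a second week. The protocol gives no rate for either, so the number affected lies between 0 and roughly 10 (12 at most on these figures).

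**Does the protocol count episodes elsewhere?** Yes. The hand-foot syndrome table for capecitabine in 8.4.2 heads its columns by first to fourth appearance of the toxicity. This supports reading the 8.4.5 text as counting recurrences. It does not show which trigger was intended for cetuximab.

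**The case against.** The strongest answer is that the conflict depends on a figure that cannot be seen. The footnote names no dose. Its asterisk might mark a separate persistence branch (hold in the second week, hold in the third, then stop) beside a recurrence branch that carries the reductions. Such a branch would fit the 14-day delay and the limit on withheld infusions, and text and footnote would then cover different courses without conflict. This stands as a limit on certainty. It does not remove the point: the only step in the section numbered second and third is the reduction to 200 and then 150 mg/m², and the text presents the figure as a summary of the dose modifications.

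A reader might infer more than the documents support:

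- **That the footnote has cetuximab given at a reduced dose while grade 3 persists, against the restart condition.** The footnote does not say so. It could equally fix the dose to be used once the rash has settled.
- **That a three-week episode is discontinued under one rule and stepped down under the other.** If the infusions are withheld, the limit applies under both.
- **That a recurrence just before the fourth weekly dose means the last two doses are given at 200 mg/m² rather than 250.** If the fourth dose is withheld for unresolved grade 3, at most the fifth is given at the lower level. The count depends on timing and on whether the optional delay is used.
- **That about 10 patients are affected, or that these are the commonest courses.** The first is the number with any severe skin reaction; the second has no source in the protocol.
- **That sites do in fact dose differently.** Sites hold the complete flowchart. The visible wording shows that they could.

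**Conclusion.** The text of 8.4.5 and the Figure 6 footnote describe different events as the second and third step, and the protocol does not reconcile them. If the asterisk marks the 200 and 150 mg/m² steps, the two triggers give different permanent doses both for a rash that resolves and recurs and for a single episode that runs into a second week before resolving. The difference at the first step is 20% of each remaining weekly dose given, and at the second step 40%. That rests on the two stated assumptions: what the asterisk marks, and no reduction at a first episode.

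The point is worth correcting because it concerns dosing and safety of the agent under test. It is a matter of consistent dose delivery, not of the trial's statistical operating characteristics.

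**What to change.** The sponsor should reconcile the text of 8.4.5 with the Figure 6 footnote, checking the boxes of the full flowchart, so that both name the same trigger for each reduction step. The agreed wording should also fit the sentence on restarting at grade 2 or less and the limit on consecutive withheld infusions in 8.4.3 and 8.4.5. If recurrence and persistence are meant to be handled on separate branches, text and figure should both say so. Which trigger applies, and at what dose, is the sponsor's clinical decision; none is proposed here.

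The cost is one sentence or one footnote in an amendment, with a short memo to sites. Sample size and analysis are unchanged.
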